#### **8.4.2 Duration of Objective Response**

Duration of objective response is defined as the time from the first documentation of objective response that is subsequently confirmed at a visit that is  $\geq 28$  days later to disease progression or death due to any cause.

$$\text{Duration of response (months)} = (\text{earliest date of progressive disease or death due to any cause or censoring} - \text{date of first objective response} + 1) / 30.4375$$

Duration of objective response will be computed only among subjects who experience an objective response (confirmed CR or confirmed PR). For DOR per BIRC the dates of progression and censoring are shown in column PFS-EP-1 of Table 8, and for DOR per investigator the dates of progression and censoring are shown in column PFS-EP-3 of Table 8.

Duration of objective response will be analyzed using the same analysis method (Kaplan-Meier) as for the analysis on PFS for OITT and ITT populations (see Section 8.1.2.6).

#### **8.4.3 Time to Objective Response**

Time to objective response is defined as the time from randomization to the first documentation of objective response that is subsequently confirmed at a visit that is  $\geq 28$  days later to disease progression or death due to any cause.

$$\text{Time to objective response (months)} = (\text{date of first objective response} - \text{date of randomization} + 1) / 30.4375$$

Time to objective response will be computed only among subjects in the OITT and ITT populations who experience an objective response (confirmed CR or confirmed PR), and arithmetic methods (not Kaplan-Meier) will be used.

#### 8.4.4 Time to Second Disease Progression or Death (PFS2)

The time to second disease progression or death (PFS2) is defined as the time from randomization to the date of the earliest of the following events: start of second subsequent non-radiation anti-cancer therapy, second objective disease progression, or death. For placebo subjects who have crossed over to receive cabozantinib, cabozantinib will be considered as the first subsequent therapy. For subjects randomized to cabozantinib who continue on study treatment after their first disease progression, the start date of their first subsequent therapy will be considered to be a potential event date. Subjects alive and for whom a PFS2 event has not been observed will be censored at the last time known to be alive. The definition of event dates for PFS2 is provided in the table below.

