### **7.1.2 Prohibited or Restricted Therapies**

*The following therapies are prohibited until study treatment has been permanently discontinued:*

- Any investigational agent or investigational medical device.
- Therapeutic doses of oral anticoagulants (eg, warfarin or other coumarin-related agents, direct thrombin or direct FXa inhibitors, or antiplatelet agents such as clopidogrel, or chronic use of aspirin above low dose levels for cardioprotection per local applicable guidelines).
- Any nonprotocol systemic anticancer treatment (eg, chemotherapy, immunotherapy, radionuclides, drugs or herbal products used specifically for the treatment of DTC).

*The following therapies should be avoided until study treatment has been permanently discontinued or until otherwise specified:*

- Local anticancer treatment including palliative radiation, ablation, embolization, or surgery with impact on tumor lesions should not be performed until radiographic progression per RECIST 1.1 has been established. If clinically unavoidable the investigator should consult the Sponsor prior to the procedure for safety guidance.
- Erythropoietic stimulating agents (eg, epoetin alfa and darbepoetin alfa) should not be used based on a report of increased risk of tumor recurrence/progression associated with erythropoietin (Wright et al 2007).
- Concomitant medications that are known to prolong the QTc interval should be avoided in subjects who receive cabozantinib until they have permanently discontinued cabozantinib treatment (refer to <http://www.qtdrugs.org> for a list of drugs which have the potential to prolong the QTc interval).
- Chronic co-administration of cabozantinib with strong inducers of the CYP3A4 family (eg, phenytoin, carbamazepine, rifampin, rifabutin, rifapentine, phenobarbital, and St. John's Wort) may significantly decrease cabozantinib concentrations and should be avoided. Selection of alternate concomitant medications with no or minimal CYP3A4 enzyme induction potential is recommended. See Appendix E for further details.
- Caution must be used when discontinuing treatment with a strong CYP3A4 inducer in a subject who has been concurrently receiving a stable dose of cabozantinib, as this could significantly increase the exposure to cabozantinib.

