## **Appendix B: Crossover Phase - Eligibility Criteria and Schedule of Assessments**

At the time of investigator-determined radiographic progression per RECIST 1.1, investigators may request from the Sponsor's medical monitor (or designee) confirmation of BIRC-determined radiographic PD.

For subjects with BIRC-confirmed radiographic progression:

- Upon authorization from Sponsor's medical monitor (or designee), investigators may unblind the individual subject via the IRT system
- Unblinded subjects randomized to placebo have the following options:
  - Such subjects may be provided by the Investigator the opportunity, if eligible (see criteria below), to enter the Crossover Phase to receive cabozantinib and undergo study assessments as defined herein.
  - Such subjects who are ineligible or opt not to crossover to receive cabozantinib are to have study treatment discontinued and proceed with post-treatment assessments as described in Appendix A.
- Unblinded subjects randomized to cabozantinib may continue on study treatment if the investigator believes the subject is still deriving clinical benefit. Study assessments are to continue per the schedule of assessments in Appendix A.

Subjects without radiographic progression per BIRC will not be unblinded and are to continue to receive blinded study treatment and undergo study assessments according to the schedule in Appendix A.

Screening of placebo subjects for crossover to cabozantinib will continue until the transition of the study to the Maintenance Phase.

Assessments for the Crossover Phase are outlined in Table 20-1.

Data for the Crossover Phase, will be summarized separately and will not be included as part of the primary evaluation of either arm.

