### **Eligibility Criteria for Crossover to Cabozantinib Following Treatment with Placebo**

(Note that the numbering of the criteria is maintained from the start of the study [Section 4.2 Inclusion Criteria and Section 4.3 Exclusion Criteria]. “Not applicable” rows below refer to eligibility criteria from the start of the study that are not relevant for the Crossover Phase as these subjects have either already fulfilled the criteria upon study entry, or the criteria are not a requirement for the Crossover Phase.)

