| Survival, post-study treatment (Section 5.4 and 5.7.11)                    |   |   |             |             |             |             |                      |   | Every 12 wks       |

CAPN, chest/abdomen/pelvis/neck; CRF, case report form; CT, computed tomography; ECG, electrocardiogram; ECOG, Eastern Cooperative Oncology Group; ICF, informed consent form; IRB/EC, Institutional Review Board/Ethics Committee; MRI, magnetic resonance imaging; PT/INR, prothrombin time/international normalized ratio; PTT, partial thromboplastin time; RECIST, Response Evaluation Criteria in Solid Tumors; UPCR, urine protein/creatinine ratio.

- a Screening assessments must be reviewed by the investigator before crossover to confirm that the subject meets the crossover eligibility criteria. Only subjects randomized to the placebo arm who opt to crossover to receive cabozantinib will undergo crossover screening. Subjects randomized to the cabozantinib arm and subjects randomized to the placebo arm who do not crossover will continue their original study assessments per Appendix A according to the Week and Day from time of first dose of blinded treatment.
- b In addition to informed consent obtained for the main study, informed consent specific for the Crossover Phase must be obtained. Informed consent may be obtained greater than 28 days prior to crossover, but must be provided before any study-specific procedures are performed; however evaluations performed as part of routine care prior to informed consent can be utilized as screening evaluations if permitted by the site's IRB/EC policies. The Investigator must ensure that the subject consents on the most recent version of the ICF.
- c Interval medical history will be collected for subjects randomized to the placebo arm who undergo screening for crossover and who have discontinued blinded study treatment > 30 days prior to W1D1 of crossover. All adverse events that were experienced ≤ 30 days after the date of decision to discontinue any study treatment (blinded or unblinded) will be collected on the adverse event CRF.
- d Additional ECGs should be performed if clinically indicated

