**Table 11: PFS2 Event Dates**

| Randomized Treatment | Condition  | PFS2 Event date  |
|----------------------|--|--|
| Placebo              | No Crossover   | Earlier of:
a) Death
b) 2 nd documented date of progression
c) Start date of 2 nd Non-protocol Anti-cancer therapy (NPACT)                                |
|                      | Crossover  | Earlier of:
a) Death
b) 1 st documented date of progression after initiation of cabozantinib
c) Start date of 1 st NPACT after initiation of cabozantinib |
| Cabozantinib         | Discontinue after 1 st documented disease progression     | Earlier of:
a) Death
b) 2 nd documented date of progression
c) Start date of 2 nd NPACT   |
|                      | Continue on open-label cabozantinib after 1 st documented | Earlier of:
a) Death
b) 1 st documented date of progression after starting open-  |

|  |                     |   |
|--|---------------------|---|
|  | disease progression | label cabozantinib
c) Start date of 1 st NPACT after starting open-label cabozantinib |
|--|---------------------|---|

The analysis of PFS2 will include all subjects in the ITT population done contemporaneously with the primary PFS analysis.

The summaries (median and 95% CI for median, stratified and unstratified HRs and their 95% CI) and graphs described in Section 8.1.2.6 will be generated for PFS2. Log-rank p-values will be calculated and will be presented for descriptive purposes; formal inferences will not be drawn.

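### PFS2 counts cabozantinib as the first subsequent therapy in every crossed-over placebo subject, even when a non-protocol therapy came before it

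*Combined protocol and SAP*

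**What the plan says.** SAP Section 8.4.4 defines PFS2 for all ITT subjects as the time from randomization to the earliest of "start of second subsequent non-radiation anti-cancer therapy, second objective disease progression, or death". The same paragraph then adds, with no exception: "For placebo subjects who have crossed over to receive cabozantinib, cabozantinib will be considered as the first subsequent therapy".

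Table 11 turns this into event dates. In the placebo Crossover row the event is the earliest of death, the first "documented date of progression after initiation of cabozantinib", and the start of the first "NPACT after initiation of cabozantinib". Before cabozantinib starts, nothing but death can count. The placebo No Crossover row follows the general definition: death, second progression or second NPACT.

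Four places in the protocol bear on what can happen before crossover:

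- Appendix B, Table 20-1, footnote c asks for an interval medical history from placebo subjects "who have discontinued blinded study treatment > 30 days prior to W1D1 of crossover", so a gap off treatment is foreseen.
- Appendix B also says: "Screening of placebo subjects for crossover to cabozantinib will continue until the transition of the study to the Maintenance Phase".
- In the crossover eligibility list, exclusions 1 to 3 (prior agents, kinase-inhibitor washout, antibody and chemotherapy washout) are marked as not applicable. The preamble gives two possible reasons: the subject already met the criterion at study entry, or "the criteria are not a requirement for the Crossover Phase".
- Section 7.1.2 restricts NPACT with the words "The following therapies are prohibited until study treatment has been permanently discontinued". The bar ends when study treatment ends for good.

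**The concern.** The crossover sentence fixes the position of cabozantinib in the treatment sequence without looking at the sequence. If a placebo subject stops blinded treatment, takes a non-radiation NPACT and later crosses over, cabozantinib is the second subsequent therapy. Under the general definition its start is itself a PFS2 event, and a progression on the NPACT would be an earlier one. The Crossover row ignores both. An event that has already occurred is removed because of a later treatment decision.

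At stake is the descriptive PFS2 comparison (medians and hazard ratios). SAP Section 4.9 says PFS2 was added on the recommendation of EU regulators as an intermediate clinical endpoint. An error confined to one arm distorts that comparison.

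**Working it through.** The documents give no sample size, event count or expected value for PFS2, so there is no figure to reproduce. The check applies the two rules to the same subject history and then looks at the possible size.

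**Worked case (placebo subject, months from randomization).** First progression 4, NPACT 5, second progression 8, cabozantinib 9, progression on cabozantinib 18.

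- General definition: second progression at 8; second subsequent therapy (cabozantinib) at 9. PFS2 = min(8, 9) = 8.
- Table 11, No Crossover row, had this subject never crossed over: second progression at 8. PFS2 = 8.
- Table 11, Crossover row: first progression after cabozantinib. PFS2 = 18.

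If no second progression were documented on the NPACT, the general definition would give 9 (cabozantinib start) and the Crossover row still 18.

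**Direction.** With a prior NPACT, the general-definition event is never later than cabozantinib start. The Crossover-row event, or the censoring that replaces it, falls after cabozantinib start. The Crossover row can therefore never shorten PFS2 in these subjects.

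**Number of subjects (illustration).** Inputs from SAP Section 2.4: 100 placebo subjects, median PFS 5.5 months, uniform accrual over 15 months, analysis near month 20. With λ = ln 2 / 5.5 = 0.126, the share with a PFS event by month 20 is

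1 − (e^(−5λ) − e^(−20λ)) / (15λ) = 1 − (0.533 − 0.080) / 1.890 ≈ 0.76.

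That is about 76 subjects. At 50–80% crossover uptake (assumption), 38 to 61 cross over, before allowing for lags and deaths. If 5–10% of those had an intervening NPACT (assumption without a source in the documents), 38 × 0.05 ≈ 2 to 61 × 0.10 ≈ 6 would be affected. If none did, the number is zero.

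**Effect on the placebo median (illustration).** Deaths and censoring are ignored. Assumed medians: 5.5 months to first progression, 9 months on cabozantinib after crossover, 3 months from interim NPACT to second progression, and 3 months to second progression in those who never cross over. Cabozantinib is assumed to start 1 month after the second progression. Each cell shows the general definition, then Table 11, in months.

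| Share with interim NPACT | 50% cross over | 70% cross over | 90% cross over |
|---|---|---|---|
| 0% | 13.09, 13.09 | 14.65, 14.65 | 16.41, 16.41 |
| 5% | 12.93, 13.24 | 14.35, 14.83 | 16.05, 16.70 |
| 10% | 12.72, 13.31 | 14.12, 15.07 | 15.61, 16.91 |
| 20% | 12.41, 13.58 | 13.55, 15.42 | 14.83, 17.37 |

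The shift is nil at 0%, about 0.3 to 0.7 months at 5%, 0.6 to 1.3 at 10% and 1.2 to 2.5 at 20%.

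**What the cutoff does.** PFS2 is analysed with the primary PFS analysis, near month 20. A simulation of affected subjects was run with these accrual and median values, adding a 1-month lag before the NPACT and another before cabozantinib, and again ignoring deaths. Among those who cross over before the cutoff, median time on cabozantinib by then is about 3.5 months and the median observed extension about 4.5 months. Only about 16% show an extension of 9 months or more, and about two thirds are censored. The commoner effect is an event turned into a censored observation.

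**The case against.** The strongest objection is that the path is inferred from silence. No section describes placebo, then NPACT, then crossover. At unblinding the protocol offers crossover or discontinuation, and the usual course is confirmed progression, unblinding and prompt crossover. Footnote c concerns medical history and does not mention NPACT; a gap can also come from an adverse event or from the radiation and wound-healing waits. Marking the systemic washouts as not applicable fits drafters who assumed no therapy in between. Tumor assessments may stop at the first systemic NPACT (Protocol Section 5.7.6.1), so a subject who starts NPACT before confirmed progression may never qualify for crossover on progression.

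All of this bears on frequency, and it stands: the case is probably uncommon. It does not remove the error, because nothing bars the path and the SAP states a rule that gives the wrong date when it occurs.

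It can also be said that the crossover sentence is part of the definition and Table 11 leaves programmers no ambiguity. That is so, but the result still contradicts both the general definition and the No Crossover row for an identical history up to crossover.

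A reader might infer that any second progression ignored before crossover is likewise a placebo-only bias. Table 11 does not support that. The cabozantinib row for subjects who continue open-label also counts only progression after open-label treatment starts, and treatment past progression is allowed in both arms. Only the NPACT component is specific to placebo.

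**Conclusion.** The point holds for a non-radiation NPACT taken between blinded placebo and crossover. In such subjects the Crossover row dates PFS2 later than the SAP's own general definition does, or leaves them censored. The error is confined to the placebo arm and can only lengthen placebo PFS2, so it works against cabozantinib and cannot create a false claim of benefit.

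Its size is not known from the documents. The 2 to 6 subjects and the shifts in the median rest on assumed shares and apply only if such subjects exist. A reader might take each affected subject's extension to be the full 9-month design median; the cutoff near month 20 makes that too large for most. Nor does the point reach the trial's conclusions: PFS2 is exploratory, its p-values are descriptive, and no alpha is attached. This is a minor correction, worth making because it is cheap.

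**What to change.** Amend SAP Section 8.4.4 and Table 11 before unblinded analysis:

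1. State that cabozantinib after crossover counts as the next subsequent therapy in sequence. It is the first only if no non-radiation anti-cancer therapy was started between randomization and crossover. Keep the term non-radiation, as in the general definition, and do not narrow it to systemic therapy.
2. Add a branch to the Crossover row. If such therapy preceded crossover, the event is the earliest of death, second documented progression, and start of the second subsequent non-radiation therapy, whether that is another NPACT or cabozantinib.
3. For a second progression before open-label start with no intervening NPACT, set one rule and apply it to both the placebo Crossover row and the cabozantinib row for continued open-label treatment. The general definition would count it.
4. Report the number of affected subjects by arm.

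The cost is a few lines of SAP text and the matching programming. Protocol Section 5.4.2 already collects NPACT names and dates, and progression after systemic NPACT.

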### **5.4.2 Extended Follow-up**

Following treatment discontinuation for whatever reason, subjects will continue to be followed either via clinic visit or telephone contact approximately every 12 weeks ( $\pm$  7 days) for the following information unless the subject withdraws consent for non-interventional study assessments:

- Survival status of the subject or date of death and primary cause of death
- Receipt of NPACTs: drug or procedure name and start/stop dates
- Information on subsequent progression following systemic NPACT (eg, date of subsequent radiographic progression or last known radiographic assessment)

Radiographic disease assessments and EQ-5D-5L are to continue in the Extended Follow-Up period as necessary per the schedule for these assessments in Appendix A, unless the subject withdraws from study interventions.

Subjects will be followed until death or until the Sponsor's decision to no longer collect these data.

At each contact, the investigator (or designee) will determine if the subject died, and if so, record the date and cause of death. All efforts must be undertaken by the study sites to determine the date of death (or date subject last known alive at the time of a data cut-off). This may include, but not necessarily be limited to, telephone contacts, communication at study visits, registered letters, and reviews of local obituaries and government death records (where allowed by local regulations). If subject is lost to follow-up, multiple attempts to contact must be made and documented in the subject records.

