Radiographic tumor assessments are to continue until the later of investigator-assessed radiographic disease progression per RECIST 1.1 that is confirmed per real-time BIRC review or the date of the decision to permanently discontinue study treatment; however, radiographic tumor assessments may cease at the time of first systemic NPACT, if given before these milestones occur. Bone scan evaluations will end on the date of last CT/MRI scan. If the bone scan schedule does not coincide with the last CT/MRI scan, no additional bone scan is needed after the last CT/MRI scan has been performed.

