### **4.1 Analyses, Reports, Treatment Periods and Summary Groups**

Up to four analyses milestones are planned over the course of the study, with treatment periods shown below:

1. Primary ORR + interim PFS [Blinded treatment period]
2. Final PFS [Blinded treatment period except for subjects who were individually unblinded for potential crossover]
3. Safety update for 120-day report [Blinded treatment period]
4. Final safety update, upon initiation of the Maintenance Phase [Blinded and Open-label treatment periods]

Up to four study reports are planned:

1. Primary clinical study report (CSR), written the first time the null is rejected for either of the primary efficacy endpoints, or if all primary testing is completed without rejection of either null.

2. CSR efficacy addendum, written if analyses #2 is successful subsequent to success of ORR in analysis #1
3. 120-Day safety update written to include results from analysis #3
4. Final CSR safety addendum, written to include analysis #4

Details on the interim analysis of PFS and the control of type 1 error are provided in [Sections 8.3](#) and [8.2](#).

Data collected for this study can be grouped by the following two treatment periods in which it was obtained:

**Blinded Period:** In this phase of the study subjects receive either cabozantinib or placebo and the treatment identity is unknown to them.

**Open-label Period:** At the time of investigator-determined radiographic progression per RECIST 1.1 that is confirmed by BIRC subjects may be individually unblinded. Further, the entire study may be unblinded if the PFS endpoint results are sufficiently compelling. At such time, subjects will have the following options:

- Subjects randomized to the placebo arm may discontinue study treatment (if still on treatment) or, if eligible, cross over to receive cabozantinib after unblinding
- Subjects randomized to the cabozantinib arm still receiving study treatment may discontinue study treatment or continue to receive cabozantinib

For both treatment arms the date of registration for treatment with unblinded cabozantinib recorded in the IRT will define the start of the Open-Label Period.

Efficacy summaries (other than OS) will be based on data obtained in the Blinded Period for the two treatment arms – cabozantinib and placebo.

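### PFS2 censors event-free subjects at last known alive although scheduled imaging can end before a second progression, and SAP 4.1 shuts out data that PFS2 needs

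*Combined protocol and SAP*

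**What the plan says.** SAP 8.4.4 defines PFS2 as time from randomization to the earliest of "start of second subsequent non-radiation anti-cancer therapy, second objective disease progression, or death". For everyone else it states: "Subjects alive and for whom a PFS2 event has not been observed will be censored at the last time known to be alive". Table 11 sets the event dates in four rows. Two of them, placebo subjects who cross over and cabozantinib subjects who continue open-label after progression, count the first progression or first NPACT after that cabozantinib begins.

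On imaging, Protocol 5.7.6.1 says: "Radiographic tumor assessments are to continue until the later of investigator-assessed radiographic disease progression per RECIST 1.1 that is confirmed per real-time BIRC review". The second of the two milestones is the decision to stop study treatment. The section adds: "radiographic tumor assessments may cease at the time of first systemic NPACT, if given before these milestones occur". After that, Protocol 5.4.2 has sites make contact about every 12 weeks. They ask about survival, NPACT and progression following systemic NPACT, for example the "date of subsequent radiographic progression or last known radiographic assessment".

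On which data count, SAP 4.1 says: "Efficacy summaries (other than OS) will be based on data obtained in the Blinded Period". Table 3 of the SAP lists only that period.

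SAP 4.9 calls PFS2 an exploratory analysis, added on the advice of EU regulators because OS is not a primary endpoint. SAP 8.4.4 reports medians, hazard ratios and confidence intervals without formal inference.

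**The concern.** A second objective progression can only be seen if someone looks for it. A subject who stops treatment at confirmed progression has passed both imaging milestones, so no further scan is scheduled. That subject can still be reached by telephone and found alive, and the SAP rule then credits the whole interval as free of second progression. Primary PFS does not work this way: SAP 8.1.2.4 censors event-free subjects at their last tumor assessment. SAP 8.4.4 gives no reason for the different rule.

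The chance of being scanned after first progression also depends on the treatment path, and the paths differ by arm. The distortion therefore need not cancel in the hazard ratio. In addition, a literal reading of SAP 4.1 would remove the very events on which two of Table 11's rows rest. At stake is the credibility of the endpoint added to help regulators interpret a trial in which OS is not primary.

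**Working it through.** **No stated figure.** The plan gives no event count, power or hazard ratio for PFS2, so there is nothing to reproduce.

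**Mechanism.** Let first progression fall at t1, an unscanned second progression at t2, and the last contact alive at c, with t1 < t2 < c and no second therapy. The SAP records c event-free months. Of these, c − t1 were unassessed and c − t2 came after the true event. If the second progression is captured, the error is zero.

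**Scheduled imaging after first confirmed progression, by path**

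| Path | Scheduled imaging | Source |
|---|---|---|
| Placebo, crosses over | Every 8 weeks in the first 12 months, then every 12 weeks; but standard of care in another section | Protocol 5.7.6.2 and Table 20-1; against Protocol 5.3 |
| Placebo, does not cross over | None (treatment stopped) | Protocol 5.3, 5.7.6.1 |
| Cabozantinib, continues | Appendix A schedule while on treatment | Protocol 5.3 |
| Cabozantinib, stops at progression | None | Protocol 5.7.6.1 |

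Each arm has a scanned and an unscanned path. The shares taking each path are not given.

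**Simulation.** Inputs from the documents: 300 subjects allocated 2:1, accrual over 15 months, cut-off at the 193rd PFS event, and median OS of 35 months (phase 2 study in the synopsis). Assumptions: median PFS of 7.5 months in both arms (no true difference), median 5.5 months from first to second progression, and next therapy a median of 6 months after an unrecorded second progression. Let q be the share of second progressions captured without scheduled imaging. There were 300 replicates per scenario, and the hazard ratio (cabozantinib to placebo) came from a Cox model.

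| Placebo crossover / cabozantinib continuation | q | HR, full ascertainment | HR, SAP rule | Undetected months per subject, cabozantinib vs placebo |
|---|---|---|---|---|
| 80% / 30% | 0 | 1.00 | 0.76 | 0.61 vs 0.17 |
| 80% / 30% | 0.5 | 1.01 | 0.89 | 0.32 vs 0.09 |
| 50% / 50% | 0 | 1.00 | 0.99 | 0.44 vs 0.44 |
| 30% / 60% | 0 | 0.99 | 1.16 | 0.36 vs 0.61 |
| 30% / 60% | 0.5 | 0.99 | 1.08 | 0.17 vs 0.30 |

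At q = 1 the SAP rule matches full ascertainment in every scenario. With the design medians (9.0 vs 5.5 months) and q = 0, the hazard ratio moved from 0.765 to 0.615 at 80%/30%, and from 0.787 to 0.992 at 30%/60%.

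**Effect of the replacement rule.** Separate runs, also with assumed rates, no true difference and no off-schedule capture, gave 0.73 to 0.74 (80%/30%) and 1.15 to 1.23 (30%/60%) under the SAP rule. Censoring at the last known radiographic assessment moved these to about 0.89 to 0.90 and 1.03 to 1.08. A harsher version gave 0.69 at 80%/30%: there, every subject without recorded progression left follow-up at the first-progression scan, and later deaths and therapies were discarded. The gain therefore depends on pulling back only subjects with no PFS2 event.

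**SAP 4.1 against Table 11.** SAP 4.1 starts the Open-Label Period at registration for unblinded cabozantinib and confines non-OS efficacy summaries to the period before it. Two of Table 11's four rows date events after that registration. Both instructions cannot be followed.

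**The case against.** A reader might infer that the rule inflates PFS2 in favour of cabozantinib, because placebo subjects who cross over are scanned and cabozantinib subjects who move to other therapy are not. The documents do not support that. Cabozantinib subjects may continue after progression and stay on the imaging schedule, placebo subjects who do not cross over have none, and the passages on crossover imaging disagree. With no rates given, the bias can run either way. For the same reason no particular gain in median PFS2 can be attached to the rule, especially as second subsequent therapy also ends PFS2 and limits the unobserved time.

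Other points against acting have some force:

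- **Second progression is not wholly unobserved.** Contacts collect progression after systemic NPACT, and the permission to stop scanning is only a permission. This stands. The weakest coverage is for subjects who stop at progression and receive no systemic NPACT, since Protocol 5.4.2 does not clearly cover them.
- **Last-assessment censoring can itself be informative.** This stands, and the 0.69 result shows how it can go wrong. The proposed form did better in both unbalanced scenarios but did not reach 1.0.
- **SAP 4.1 is a general convention and Table 11 is specific, so the intent is clear.** That makes it a drafting conflict, but still one that a programmer could resolve wrongly. SAP 4.3 and 8.1.1.6 also foresee open-label efficacy exploration, so the sentence is too narrow beyond PFS2.
- **PFS2 is exploratory and descriptive.** This is correct, and it limits the weight of the point.

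**Conclusion.** The point holds as a correctable weakness in an exploratory endpoint. The SAP counts unassessed time as free of second progression, which inflates PFS2 whenever some second progressions go uncaptured. It can also bias the hazard ratio: against a true value of about 1.0, the runs tabulated above ranged from 0.76 to 1.16 under the SAP rule. These figures rest on assumed crossover, continuation, capture and timing rates and show only that the sign is open. The mechanism and the conflict between SAP 4.1 and Table 11 need no assumptions. The primary endpoints and the type I error plan are untouched.

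**What to change.** 1. In SAP 8.4.4, censor subjects without a PFS2 event at the last known radiographic assessment, including off-schedule scans whose dates are collected under Protocol 5.4.2. Deaths and second subsequent therapies remain events. Keep last-known-alive censoring as a sensitivity analysis. Report completeness of progression assessment by arm, and state that last-assessment censoring reduces the bias but does not remove it.
2. In SAP 4.1, extend the exception for OS to OS and PFS2.
3. Reconcile Protocol 5.3 with Protocol 5.7.6.2 and Table 20-1 on imaging after crossover.

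The cost is SAP wording, one completeness table, a protocol clarification and somewhat less PFS2 follow-up time. Where no scan follows first progression, the censoring date falls back to that scan. SAP 4.9 allows such a revision before unblinded analyses, and SAP 9.9 already foresees an amendment.
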